To assess the potential for telerehabilitation to enhance visual function by providing remotely-delivered LVR training to use magnification devices (i.e., hand-held or stand optical magnifiers, electronic magnifiers). Following basic LVR (i.e., one in-office training session) for new magnification device(s), we aim to determine if there is additional gain in visual functioning by randomizing subjects (2:1) to telerehabilitation or additional in-office LVR (active control). This will help provide estimates of effect size to plan a future larger-scale randomized controlled trial. We will compare visual function changes with the Activity Inventory questionnaire and validated reading tests in 60 LV patients with central vision loss due to any ocular disease recruited from 10 centers. Participants will be assessed before and after two consecutive periods: (1) no further training will be provided for one month after a single LVR training session (i.e., basic LVR), followed by (2) up to three LVR sessions over a three month period either via telerehabilitation (n=40) in the participants' homes with study loaner equipment (iPad/smartphone, stand, reading cards) via remote control assistance, or in-office LVR (active control; n=20). Multiple sessions will be conducted if the LVR provider deems the participant is not completely proficient with their magnification device. We will determine which patient characteristics and/or magnification devices are most likely to benefit from telerehabilitation, to be targeted in a future, larger-scale, phase III trial.

The primary goal of this proposal is to refine the methods and procedures for implementing these innovative technologies for LVR, in order to develop future protocols for randomized controlled trials. In the future, we envision that telerehabilitation could improve efficiency and patient outcomes by changing the method by which follow-up LVR services are provided. This is a high priority given the increasing prevalence of LV, paucity of LVR providers, and barriers related to transportation and geography.

Background and Significance: Provide a summary of the background for this study and explain how it will contribute to existing knowledge.

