Our primary outcome measure, the Activity Inventory questionnaire, and the secondary outcome measure, the Sustained Silent Reading test by Ramulu et al., will be administered by phone by a UCLA research assistant at baseline (time of study entry), one month following receipt of the new magnification device, and four months after receipt of the magnification device (at time of study completion). The SF-36 general health questionnaire, Telephone Interview for Cognitive Status (TICS), Geriatric Depression Scale, and Hospital Anxiety Depression Scale questionnaires will be administered by phone by a UCLA research assistant at baseline (time of study entry), and four months after receipt of the magnification device (at time of study completion). The MNread test will be administered by the OD/OT provider at each in-office visit and/or during telerehabilitation sessions. Within 24 hours of each telerehabilitation session or in-office rehabilitation session, the UCLA research assistant will administer a satisfaction survey by phone. To characterize participants' baseline level of visual impairment, we will gather information from a medical record review from each our sites, in which we will record the results from validated visual acuity and contrast sensitivity tests at the initial in-office visit. These vision tests are used as part of standard of care.

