Multiple regression analyses will assess if effect sizes for the telerehabilitation and in-office LVR control group (i.e., changes in the outcomes: Activity Inventory score, reading speed) are related to the number of telerehabilitation sessions, patient demographics, visual acuity, contrast sensitivity, diagnosis, or scores on the SF36, Telephone Interview for Cognitive Status (TICS), Geriatric Depression Scale, or Hospital Anxiety Depression Scale questionnaires. We will apply advanced statistical methods (e.g., multilevel models) for missing data. We will perform a Rasch analysis of our Activity Inventory data in comparison to a very large database of LV patients (several thousand) who have completed the Activity Inventory. Goals and activities have their item measures, and the fit properties of the Activity Inventory from the database of previous responses can be used to convert raw scores into person measures. In the event of non-normally distributed data, we will use a binary outcome (proportion of subjects with improvement greater than 0.14 logits) to compare changes between telerehabilitation and in-office LVR for the Activity Inventory domains using chi-square tests and logistic regressions.

Sample Size calculation: We plan to enroll and compare findings for two equal sized groups based on visual acuity (VA); i.e., those better or worse than 20/63. A sample size calculation for matched pairs t-test revealed that 18 subjects in each of the 2 groups would detect a within-subject mean improvement of 0.14 logits on the Activity Inventory (primary outcome) following telerehabilitation (equivalent to 1-line or 0.1 logMAR VA), when considering a standard deviation of 0.17 logits for the differences, power of 0.80 and 0.05 type I error probability. We will aim to enroll a total of ~40 subjects randomized to telerehabilitation (given our 2:1 randomization plan), and aim to have a total of ~20 active controls randomized to receive in-office LVR. We will determine the effect sizes for basic LVR (one session in-office as part of standard of care), telerehabilitation and additional in-office LVR for changes in the Activity Inventory and reading outcomes.

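### No stated arm comparison or regression adjusts for the starting Activity Inventory or reading score, although it is collected; adjusting the randomised comparison would usually narrow its interval at almost no cost

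*Combined protocol and SAP*

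**What the plan says.** The Statistics and Data Analysis section obtains effect sizes for basic rehabilitation, additional in-office rehabilitation and telerehabilitation by comparing each follow-up score with the score before any rehabilitation.

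Its multiple regressions take change as the dependent variable ("i.e., changes in the outcomes: Activity Inventory score, reading speed"). The predictor list has nine entries: number of sessions, demographics, visual acuity, contrast sensitivity, diagnosis, SF-36, TICS, Geriatric Depression Scale and Hospital Anxiety Depression Scale. The participant's own starting score is not among them.

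The one comparison of arms that is spelled out applies if the data are not normally distributed. Improvement above 0.14 logits becomes a yes/no outcome, compared "using chi-square tests and logistic regressions". No covariates are named. For normally distributed data no between-arm model is given. Multilevel models are mentioned only as a way of handling missing data.

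The Outcome measures section schedules the Activity Inventory and the Sustained Silent Reading test "at baseline (time of study entry), one month following receipt of the new magnification device", and again at four months. The Research Plan and Methods section places randomisation after the one-month run-in. Each participant therefore has two scores on both instruments before the randomised training starts.

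**The concern.** The Specific Aims ask the trial for two things: effect-size estimates to plan a larger randomised trial, and an indication of which patients benefit most. How the starting score is handled bears on both.

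For the arm comparison, a raw change score subtracts the whole starting score, whereas the best linear correction subtracts only the part that predicts the final score. The excess is noise, and it widens the interval around the estimate that the next trial would be built on.

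For the predictor question, someone who scores low at the start partly by chance will tend to rise later. A predictor that shares that chance error will then appear related to change without having any real effect. The SF-36, TICS and the two mood scales are collected by phone at the same time point as the starting score, so shared error is plausible for them. A false lead here could misdirect who is targeted in the later trial.

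**Working it through.** **Inputs from the Sample Size calculation.** Improvement 0.14 logits; SD of within-subject differences 0.17 logits; about 40 participants in telerehabilitation and about 20 in-office; "power of 0.80 and 0.05 type I error probability". Sidedness is not stated and is taken as two-sided.

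**Assumptions not in the documents.** The correlation rho between starting and final score; equal variances at both times; SD of change 0.17 in both arms.

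**The plan's own figure.** The text reads: "A sample size calculation for matched pairs t-test revealed that 18 subjects in each of the 2 groups". For a paired t-test with effect 0.14/0.17 = 0.82, noncentral-t power is 0.81 at n = 14 and 0.908 at n = 18. So 14 suffices for power 0.80. Eighteen corresponds to power 0.90, or to 14/(1 − 0.20) = 17.5, rounded up, under a 20% dropout that is not stated. The stated number is larger than its inputs need. That is a separate matter, and nothing below depends on it.

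**Unadjusted arm contrast.**
- SE = 0.17 × √(1/40 + 1/20) = 0.17 × 0.2739 = 0.0466
- 95% half-width = t(58) × SE = 2.0017 × 0.0466 = 0.0932 logits

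**Adjusted arm contrast.** With score variance s², change has variance 2s²(1 − rho), and the residual after adjustment has variance s²(1 − rho²). The ratio is (1 + rho)/2. Estimating the slope costs a factor of about 1 + 1/56. The half-width is 2.0025 × 0.17 × √[(1 + rho)/2 × 57/56] × 0.2739.

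| Assumed rho | Implied SD of score at one time | Variance ratio, slope cost included | Half-width | Power for a 0.10-logit arm difference |
|---|---|---|---|---|
| change score | – | 1 | 0.0932 | 0.56 |
| 0.5 | 0.17 | 0.763 | 0.0815 | 0.68 |
| 0.7 | 0.22 | 0.865 | 0.0867 | 0.62 |
| 0.9 | 0.38 | 0.967 | 0.0917 | 0.57 |
| 0.95 | 0.54 | 0.992 | 0.0929 | 0.56 |

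The implied SD is 0.17/√(2(1 − rho)). The variance ratio reaches 1 at rho = 2 × 56/57 − 1 = 0.965. Above that, adjustment costs less than 2% of variance.

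**Predictors.** Take a predictor with no real effect.
- *It correlates 0.5 with the observed starting score.* Its correlation with change is −0.5 × √((1 − R)/2), where R is the reliability of the score. For R of 0.5, 0.7 and 0.85 this is −0.25, −0.19 and −0.14. By Fisher's z at n = 40, it would reach p < 0.05 in about 34%, 22% and 13% of trials. Adding the starting score removes the false slope.
- *It correlates 0.5 with the stable trait only.* In simulation (2,000,000 subjects per scenario, score SD set to 1), the change-score slope is zero. The adjusted model now shows a false slope of 0.20, 0.15 and 0.09 for the same reliabilities.

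Neither model is safe for every predictor on the list.

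**The case against.** The plan's main quantity is within-arm. Its sample size is a matched-pairs calculation, and it reports effect sizes per intervention. Raw change is the natural measure for that, and adjustment does not improve it. This stands, and it is why raw change should be kept.

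A reader might infer that the plan rules out adjustment. It does not: the covariates of the logistic and multilevel models are simply not stated. A multilevel model carrying the starting score as a repeated outcome could recover part of the information. What can be said is that no adjustment is stated, which leaves the choice open until the data are seen.

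A reader might also infer that chance imbalance between arms of 40 and 20 biases the comparison. Under randomisation it does not. At rho 0.5, a one-standard-error imbalance shifts the change contrast by 0.023 logits, but 0.023² is 25% of 0.0466². That is exactly the share of variance that adjustment removes at rho 0.5 before the slope cost, so it is the same loss and not a further harm.

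The gain depends on a correlation that nobody has supplied. If scores vary widely between people while change has SD 0.17, rho is high and little is gained: a cross-sectional SD of 1.0 implies rho of about 0.986 and no gain. This stands.

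Finally, the plan's reading speed may mean the MNread maximum reading speed. MNread is given at visits and sessions, not at entry, month 1 and month 4, so the remedy is limited to the two instruments on that schedule.

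**Conclusion.** The point holds as a low-cost improvement in efficiency and as a gap in specification. The stated analyses use change from the score before rehabilitation, none is said to adjust for the starting score, and two scores on each instrument are available before the randomised training.

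For the arm contrast, the variance saved is about 24% at rho 0.5, 13% at 0.7, 3% at 0.9 and 1% at 0.95, and nothing near 0.965. These figures rest on equal variances, an SD of change of 0.17 in both arms and the planned 40 and 20. The direction is secure for any rho below about 0.965; the size is unknown.

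For the predictor question, it would be tempting to conclude that every regression must include the starting score. The calculations do not support that. Unadjusted change can mislead for predictors sharing the starting score's error, plausibly SF-36, TICS and the two mood scales. Adjustment can mislead for predictors tied only to the stable trait, which may include age or diagnosis. Reporting both is the defensible course.

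**What to change.** In the Statistics and Data Analysis section:

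1. State that the between-arm comparison models the month-4 score on arm with the month-1 score as covariate, for the Activity Inventory and the Sustained Silent Reading test. The month-1 score is the natural choice because it closes the run-in; change from entry also carries the run-in change. A three-time-point model with arm means constrained equal before randomisation would serve as well.
2. Put the month-1 score in the logistic fallback.
3. Report the predictor regressions both with and without the starting score, and explain any predictor whose result differs between the two.
4. Keep raw within-arm change as the descriptive effect size.

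This needs no new data, visits or participants. The arm model gives up one degree of freedom and, if rho is very high, less than 2% of variance. The predictor models already have nine listed entries for about 40 and 20 participants, so one starting score should be added there, not two.

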A clinical model for LV telerehabilitation has already been implemented, in which the patient attends a video session at their local optometrist's office (not their home) with remotely located LVR providers at the Buffalo VA in NY. It is important to conduct research to document changes in patient outcomes following telerehabilitation, to provide evidence-based practice recommendations for this modality and future insurance reimbursement. Our eventual goal is to conduct a randomized controlled trial of telerehabilitation for LV compared to active in-office LVR (possibly an equivalence trial) to improve patients' visual function and reduce magnifier device abandonment. Given the projected dramatic increase in the expected number of people with LV over the next several decades, it is imperative to validate creative solutions to provide LVR to overcome economic and societal burdens caused by LV, and increase access to and quality of care for these individuals.

Premise:

There is a need for a clinical trial of telerehabilitation since the literature and a Cochrane systematic review completed by the PI and co-I, [name], revealed that telerehabilitation has rarely been applied to LV and there are no published outcomes from studies (i.e., no evidence of efficacy). The rationale for telerehabilitation is supported by previous studies indicating that transportation, geography, patients' co-morbidities and the paucity of providers are barriers to receiving LVR in-office. It is premature to propose a large-scale, phase III randomized controlled trial (RCT) at this time since the following are yet unknown: effect size (i.e., possibility of visual function enhancement), which patients and/or magnification devices are most likely to benefit, appropriate number of telerehabilitation sessions for proficiency, and feasibility of in-office LVR as an active control; the current study will assess these factors and then design an RCT based on findings.

Innovation:

There are several innovative elements in the proposed research program:

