technique (i.e., working distance, lighting) and reading fluency (i.e., speed, accuracy, print size) with their magnifier device. In addition, they will ask the participant to read or view their own materials of interest, while providing LVR training. If relevant, the providers will ask participants to demonstrate how to change the battery in the magnification device, or to walk around their home with the smartphone to show the illumination levels in places where they use their magnifier. We will continually assess the telerehabilitation survey responses we will collect from both the LVR providers from our clinical centers and participants, in order to resolve any reoccurring problems related to Internet connectivity, videoconference portal, hardware devices, or audio/visual quality.

Hypothesized Outcomes, Sample Size Calculation and Data Analyses

Our outcomes that are questionnaires or reading tests will be assessed by phone by a different UCLA research assistant at each evaluation. It is not possible to mask the participants or LVR providers. The outcomes assessors will be identically trained by the PI. We successfully administered reading tests by phone in a previous study by providing the materials in a sealed envelope that the subject opens only at the test exam time. Our two interventions (telerehabilitation versus additional in-office LVR) may have similar effects since the same LVR principles will be applied at the same planned schedule of sessions; however, it is possible that telerehabilitation may be more beneficial if compliance with scheduled sessions is better than in-office LVR and/or if home-based training is advantageous in the patient's own environment with relevant tasks of interest; on the other hand, there may be aspects of LVR training that work better in-person and in-office. In-office LVR or at-home LVR with a therapist in-person are currently considered standard of care. All participants will receive standard of care since they will all receive one in-office LVR training session prior to randomization.

Outcome measures

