Per study visit/session to receive telerehabilitation or training in-office = approx. one hour

Per study telerehabilitation session to complete follow-up survey = approx. 15-30 minutes

Per study session to complete questionnaire outcome measures by phone = approx. 2-3 hours

Total anticipated time commitment per subject = approx. 8-15 hours over 4 months

Statistics and Data Analysis: Describe the proposed statistical procedures or descriptive analyses for the study. If applicable, indicate how the sample size was determined.

Data analyses: Data management will be an ongoing task for the PI.

Descriptive statistics will be used to summarize the study data and findings. We will determine the effect sizes for basic LVR (one session in-office as part of standard of care), additional in-office LVR (active control), and telerehabilitation for changes in the Activity Inventory and reading outcomes by comparing the scores at each follow-up to baseline (pre-LVR). For the Activity Inventory questionnaire, we anticipate that the reading domain may have the largest magnitude of change since magnification devices are most often used for reading tasks, which is the chief complaint of most LV

patients. For the MNread test, we will primarily focus our analyses on reading acuity and maximum reading speed. Separate analyses (sub-groups) for all outcomes will be used to compare outcomes for participants with hand-held or stand-based magnifiers (optical or electronic) versus spectacle-based high add power magnification (hands-free).

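### The between-arm Activity Inventory comparison moves to a responder proportion on an undefined non-normality trigger, and no between-arm estimate in logits is named in either case

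*Combined protocol and SAP*

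**What the plan says.** The combined protocol and SAP names the Activity Inventory as primary outcome (Outcome measures) and assesses it "at baseline (time of study entry), one month following receipt of the new magnification device, and four months after receipt of the magnification device".

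Under Statistics and Data Analysis, Data analyses, the plan contains three relevant elements:

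- **Effect sizes.** The plan lists "effect sizes for basic LVR (one session in-office as part of standard of care), additional in-office LVR (active control), and telerehabilitation for changes"; these cover the primary outcome and the reading tests. Each is follow-up against baseline, so these are per-intervention changes and not a contrast between arms.
- **Regressions.** Change is related to number of sessions, demographics, vision measures, diagnosis and questionnaire scores. Randomised arm is not in the list of predictors.
- **Fallback.** "In the event of non-normally distributed data, we will use a binary outcome (proportion of subjects with improvement greater than 0.14 logits", in order "to compare changes between telerehabilitation and in-office LVR for the Activity Inventory domains using chi-square tests and logistic regressions".

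The fallback is the only between-arm comparison of the primary outcome for which a method is named. The Specific Aims state an intention to compare the groups, without a method. The 0.14-logit cut-off matches the sample size paragraph, which aims to "detect a within-subject mean improvement of 0.14 logits on the Activity Inventory (primary outcome) following telerehabilitation (equivalent to 1-line or 0.1 logMAR VA").

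**The concern.** Two things are left open.

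1. **The criterion.** The plan does not say how non-normality is judged: by which test or plot, at what threshold, on change scores or residuals, pooled or per arm, for which domain or time point. The scale of the between-arm comparison therefore depends on an unspecified judgement about the outcome data.
2. **The estimate.** If the trigger is met, the arms are compared on responder proportions. If it is not met, one may guess that the comparison is continuous, but no model, reference measure or interval is given. The fallback sentence speaks of Activity Inventory domains and does not say whether the overall person measure is covered.

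This matters because of what the study is for. The Specific Aims want effect sizes for planning a larger trial. The Background foresees a "randomized controlled trial of telerehabilitation for LV compared to active in-office LVR (possibly an equivalence trial"), and the section on hypothesised outcomes says "Our two interventions (telerehabilitation versus additional in-office LVR) may have similar effects since the same LVR principles will be applied". For that purpose the useful result is a between-arm difference in logits with its interval.

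**Working it through.** **Inputs from the plan** (Sample Size calculation): within-subject improvement 0.14 logits, SD of differences 0.17, alpha 0.05, power 0.80, about 40 telerehabilitation and about 20 in-office. **Assumptions:** the test is two-sided; 0.14 and 0.17 also serve as between-arm shift and SD, although the plan gives them only within subject; control mean change is 0, 0.07 or 0.14; the shapes below are illustrative, since the documents give no distribution.

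**The plan's own figure.** It states 18 per visual acuity (VA) group for a paired t-test. By normal approximation, n = ((1.960 + 0.842) × 0.17/0.14)² = 11.6, so 12; the exact paired t gives 14. At 18 the power is 0.91, so the stated number is on the safe side. It is a within-subject calculation, and the trigger does not touch it.

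**What the logit scale offers.** SE = 0.17 × √(1/20 + 1/40) = 0.0466. The 95% CI half-width is 2.002 × 0.0466 = 0.093 logits. Power for a 0.14 difference is 84% (t-test, normal data). A later two-arm trial would need 2 × ((1.960 + 0.842) × 0.17/0.14)² = 23.1 per arm before rounding.

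**What the responder scale does to the same shift.** The difference is P(change > 0.14 | mean m + 0.14) − P(change > 0.14 | mean m). Example, right skew (lognormal, sigma 0.6, centred and scaled to SD 0.17):

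- The lognormal mean is e^0.18 = 1.197 and its SD is √((e^0.36 − 1)e^0.36) = 0.788. A step of 0.14 logits is 0.14/0.17 × 0.788 = 0.649 on that scale.
- Mean 0: the cut-off lies at 1.197 + 0.649 = 1.846; ln(1.846)/0.6 = 1.02; P = 0.153.
- Mean 0.14: the cut-off lies at 1.197; 0.18/0.6 = 0.30; P = 0.382.
- Mean 0.28: the cut-off lies at 1.197 − 0.649 = 0.548; ln(0.548)/0.6 = −1.00; P = 0.842.

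A control mean of 0 gives 0.382 − 0.153 = 0.229; a control mean of 0.14 gives 0.842 − 0.382 = 0.460. All settings, in percentage points:

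| Shape | m = 0 | m = 0.07 | m = 0.14 |
|---|---|---|---|
| Normal | 30 | 32 | 30 |
| t, 4 df | 35 | 41 | 35 |
| Right skew | 23 | 35 | 46 |
| Left skew | 46 | 35 | 23 |

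Per-arm size for a later 80%-power trial is 7.85 × [p1(1 − p1) + p2(1 − p2)]/(p2 − p1)². It runs from about 14 (46 points) to about 55 (23 points) for one and the same logit effect.

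**Is the switch needed for validity?** No. With 40 versus 20 and no true difference, simulated type I error of a Welch test is 0.041 to 0.056 under t(4) and strongly skewed data. Regression with HC3 robust standard errors rejects in 0.035 to 0.049, and its 95% CI covers in 0.952 to 0.965.

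**Does the missing criterion matter?** Five common criteria, such as Shapiro-Wilk on residuals or absolute skewness above 1, would trigger the switch in 0–10% of trials with normal data, 23–55% with t(4), 29–63% with mild skew and 83–99% with strong skew. For moderately non-normal data, the choice of criterion can therefore decide the scale.

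**Power for a 0.14 shift** (robust regression / chi-square):

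| Shape | m = 0 | m = 0.07 | m = 0.14 |
|---|---|---|---|
| t, 4 df | 0.824 / 0.792 | 0.823 / 0.879 | 0.822 / 0.816 |
| Right skew | 0.795 / 0.473 | 0.795 / 0.760 | 0.787 / 0.958 |
| Left skew | 0.847 / 0.960 | 0.854 / 0.755 | 0.851 / 0.502 |

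Chi-square is lower in 5 of 9 settings, level (within 0.01) in 1 and higher in 3.

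**The case against.** The case for leaving the text alone has several parts.

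- **The purpose is modest.** This is a phase 1/2 study whose stated primary goal is to refine methods. Per-arm logit effect sizes are planned regardless, so an unadjusted difference and interval can be computed from arm means, SDs and sizes. That stands. What is missing is a planned reference measure, adjustment and interval.
- **The cut-off is fixed in advance and interpretable**, and a responder result suits the question of "which patients and/or magnification devices are most likely to benefit". That stands as a reason to keep it as supportive. It does not make the proportion the better main estimate: when only 30–50% of the treated arm benefits, robust regression had higher power than chi-square in 30 of 32 simulated settings and was level in 2.
- **The wide range rests on assumed shapes.** True: the extremes of 23 and 46 points come from strong skew. With t(4) data the range is 35 to 41, and with normal data 30 to 32.

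Three stronger readings are tempting, and the documents do not support them.

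- A reader might infer that the switch inflates the false-positive rate. As written, it depends on the distribution and not on the results. Simulating such a rule (Welch, switching to chi-square on residual Shapiro-Wilk p < 0.05 or absolute skewness above 1) gives type I error of 0.042 to 0.057. Inflation would need the scale to be picked after seeing both results, which the plan does not describe.
- A reader might infer that the trigger removes a planned logit comparison. None is named for normal data either.
- A reader might infer that dichotomising always loses power. The power results above are mixed.

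**Conclusion.** The point holds as a gap in specification and a weak choice of scale, of minor to moderate weight. The text leaves the trigger without a criterion and names no between-arm logit estimate or interval in either case; both can be read directly from the plan. The switch is unnecessary for valid inference at these sample sizes. The responder difference carries over poorly to a later, possibly equivalence, trial because it depends on the control mean and on shape: about 23 to 46 points for one 0.14-logit shift.

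That range assumes a between-arm SD of 0.17, a control mean of 0 to 0.14 and the illustrative non-normal shapes; it is narrower if the data are closer to normal. No stated power or sample size figure changes.

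**What to change.** Delete the normality trigger. For any distribution:

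- Report the between-arm difference in the Activity Inventory in logits with a 95% CI, from a regression of the month-4 person measure on arm and one pre-intervention measure named in advance. Baseline and month 1 are both already planned.
- Use robust standard errors. VA group may be added as a covariate; the documents describe VA groups for enrolment and comparison but do not say that randomisation is stratified by them. A Welch comparison of change can serve as the unadjusted version.
- If data are missing, fit the same contrast within the multilevel framework the plan already foresees.
- Say whether the analysis applies to the overall measure, the domains, or both.
- Keep the proportion improving by more than 0.14 logits, with its CI, as a supportive result.

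The cost is analysis text only, with no new assessments or participants. The sponsor must choose one reference measure. A logit difference is harder to explain than a responder percentage, and its power is not higher in every skewed setting.

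### The stated sample size does not follow from its inputs: a two-sided paired t-test at 0.14/0.17 logits needs 14 per visual acuity group for 0.80 power, and 18 gives 0.91

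*Combined protocol and SAP*

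**What the plan says.** The calculation is in Statistics and Data Analysis, under Sample Size calculation. The groups it concerns are not the randomised arms but "two equal sized groups based on visual acuity (VA); i.e., those better or worse than 20/63". The method, a matched pairs t-test, and the result are given in one sentence: "18 subjects in each of the 2 groups would detect a within-subject mean improvement of 0.14 logits on the Activity Inventory (primary outcome") after telerehabilitation, "when considering a standard deviation of 0.17 logits for the differences, power of 0.80 and 0.05 type I error probability".

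The paragraph then sets targets of about 40 subjects randomised to telerehabilitation and about 20 to in-office training. It does not say whether the test is one- or two-sided. It mentions no dropout allowance and no adjustment of alpha for testing two visual acuity groups. The available text contains no other sample size calculation.

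**The concern.** The effect, SD, power, alpha and test are all printed, so the required n can be recomputed with only sidedness left to assume. A standardised effect of 0.14/0.17, about 0.82, is large for a paired test, and 18 looks too many for 0.80 power.

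The patients' side of this is benign, because the mismatch errs towards more subjects. What is at stake is whether the calculation can be reproduced and reused. The Specific Aims say of the randomised comparison: "This will help provide estimates of effect size to plan a future larger-scale randomized controlled trial". If the printed SD is not the one used, or if an allowance for attrition was made but not written down, anyone who builds on this paragraph inherits a wrong assumption.

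**Working it through.** **Inputs, all from the Sample Size calculation paragraph.** Mean within-subject change 0.14 logits; SD of differences 0.17 logits; power 0.80; type I error 0.05; matched pairs t-test; n = 18 per visual acuity group. Sidedness is not stated, so both cases are tried.

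**Formula.** Standardised effect d = 0.14/0.17 = 0.8235. For n pairs, power comes from the noncentral t distribution with n − 1 degrees of freedom and noncentrality d√n, compared with the critical value of the central t.

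**Attempt to reproduce 18, two-sided 0.05.**

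| n | critical t | d√n | power |
|---|---|---|---|
| 13 | 2.179 | 2.969 | 0.778 |
| 14 | 2.160 | 3.081 | 0.813 |
| 17 | 2.120 | 3.395 | 0.890 |
| 18 | 2.110 | 3.494 | 0.908 |

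The smallest n for 0.80 is 14, or 28 over both groups against the stated 36. Eighteen is the smallest n for 0.90. The normal approximation, ((1.960 + 0.842)/0.8235)² = 11.6, gives 12 and so does not lead to 18 either.

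**One-sided 0.05.** n = 10 gives 0.775, n = 11 gives 0.815 and n = 18 gives 0.956. The requirement is 11.

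**Rounding of the inputs.** The least favourable values that still round to those printed are about 0.135 and 0.175. Sixteen subjects then suffice (0.822), and 18 give 0.869.

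**What 18 does detect.** At SD 0.17, two-sided, 18 subjects have 0.80 power for a change of 0.119 logits.

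**Unstated inputs that lead to or near 18 (two-sided).**

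- Power 0.90: exactly 18.
- Dropout of 20%: 14/(1 − 0.20) = 17.5, rounded up to 18.
- Alpha halved to 0.025 for two visual acuity groups: 17 needed (0.811); 18 gives 0.839.
- SD 0.20 instead of 0.17: 18 gives 0.799, which is 0.80 to two decimals; the smallest n with at least 0.80 is 19 (0.823).

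**The randomised contrast, for information.** The documents give no SD of change for the in-office arm, so a common SD is assumed in both arms. With 40 v 20 and 58 degrees of freedom, the standard error is SD × √(1/40 + 1/20) = SD × 0.2739, and the 95% half-width is 2.002 times that.

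| assumed SD | half-width (logits) | power for a difference of 0.14 |
|---|---|---|
| 0.15 | 0.082 | 0.92 |
| 0.17 | 0.093 | 0.84 |
| 0.20 | 0.110 | 0.71 |
| 0.25 | 0.137 | 0.52 |

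At SD 0.17, a between-arm difference of 0.133 logits has 0.80 power.

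**The case against.** The best defence is that 18 per group does detect 0.14 logits with at least 0.80 power, so the sentence is loose rather than false about what the study can do. This is a phase 1/2 study whose main goal is to refine methods, and a later trial would be planned from the observed effect and SD rather than from this paragraph. That limits the consequences. It does not make the figures agree, because 0.80 is listed as an input to the calculation that yielded 18.

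A second defence is that an allowance was made but not written down. The step from 18 + 18 = 36 to about 40 telerehabilitation subjects is a visible margin of 4, or 10% of 40, though it is not labelled as one. It comes on top of the 18 and does not explain it. Part of the document was not available for this review, so an attrition figure there cannot be excluded, but the sample size paragraph refers to none.

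A slip in the printed SD is also a live explanation, since 0.20 gives 0.799 at 18. Several routes reach 18 or come close, and the text does not identify which was used.

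Finally, the paragraph already describes the test as within-subject and never attaches 0.80 to the arm comparison. That is correct, and the between-arm figures above are an optional addition, not a second error. The plan does foresee such a comparison: if the data are not normally distributed, a binary improvement outcome would be used to "compare changes between telerehabilitation and in-office LVR for the Activity Inventory domains using chi-square tests and logistic regressions".

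**Conclusion.** The stated n and power do not belong together. At the plan's own effect, SD and alpha, a two-sided paired t-test needs 14 per visual acuity group, not 18, and 18 gives 0.908, about 11 points above the stated 0.80. Neither a one-sided test nor rounding of the inputs removes the discrepancy.

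It is conservative. At the stated inputs the within-subject tests are not under-powered. Even if the true input was an SD of 0.20, the 20 per group implied by about 40 telerehabilitation subjects would give 0.844. This is an error in the stated calculation for the primary outcome that should be corrected, but it does not threaten the design. The paired result rests only on the printed inputs and normally distributed differences. The between-arm figures also rest on an assumed common SD.

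**What to change.** Restate the calculation so that n, SD, power, alpha and sidedness agree. For example: with a two-sided 0.05 test, a mean change of 0.14 logits and an SD of differences of 0.17, 14 subjects per visual acuity group give at least 0.80 power and 18 give 0.91. If 18 came from 0.90 power, a dropout allowance, a split alpha or another SD, state that input instead. The SD should not be changed merely to reproduce 18. If the margin from 36 to about 40 is for attrition, say so.

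Optionally, add one sentence that the power figure concerns within-subject change after telerehabilitation and not the 40 v 20 contrast, and give that contrast's expected precision: a 95% half-width of about 0.093 logits if the SD is 0.17 in both arms, recalculated if the SD is corrected.

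The cost is about two sentences. Enrolment, visits, randomisation and analysis stay as they are.
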